6. STUDY TREATMENT

6.1. Investigational Product and Other Study Treatment

The term 'study treatment' is used throughout the protocol to describe any combination of products received by the subject as per the protocol design. Study treatment may therefore refer to the individual study treatments or the combination of those study treatments.

A description of the study treatments is provided in [Table 1](#)

Table 1 Study Treatment

Study Treatment		
Product name:	Albiglutide (Tanzeum in US)	Exenatide (Byetta)
Formulation/Dosage form/Delivery system:	
Lyophilized albiglutide is provided as a fixed-dose, fully disposable pen injector system for delivery of the study treatment from a prefilled dual chamber cartridge (DCC) that is an integral part of the injector pen. It is designed for manual reconstitution of the dose, priming and insertion of the pen needle (29G), and manual injection.
 
The DCC contains lyophilized albiglutide (30 mg or 50 mg). When the injector pen product is reconstituted a neutral, isotonic solution is produced. The pen delivers albiglutide in an injection volume of 0.5 mL.
	
Byetta (exenatide) is a marketed product of AstraZeneca Pharmaceuticals LP.
 
Exenatide is supplied as sterile solution for injection containing 250 µg /mL exenatide.
 
The following dose packages are available:
 
 • 5 µg dose, 60 doses, 1.2 mL prefilled pen • 10 µg dose, 60 doses, 2.4 mL prefilled pen 
Inactive ingredients include: metacresol, mannitol, glacial acetic acid, and sodium acetate trihydrate in water
 
Refer to the current PI for further

Study Treatment		
Product name:	Albiglutide (Tanzeum in US)	Exenatide (Byetta)
	30 mg pen for injection contains 40.3 mg lyophilized albiglutide and 0.65 mL 50 mg pen for injection contains 67 mg lyophilized albiglutide and 0.65 mL water Inactive ingredients include: 153 mMmannitol, 0.01% (W/W) polysobate 80, 10mM sodium phosphate, and 117 mM trehalose dehydrate in water	details.
Unit dose strength(s)/Dosage level(s):	30 mg or 50 mg	5 μ g or 10 μ g per dose
Route of Administration	SC injection in the abdomen, thigh or upper arm region. Rotation of injection sites is recommended.	SC injection in the abdomen, thigh or upper arm region.
Dosing instructions:	Study Part A: not applicable Study Part B: 30 mg, weekly for 4 weeks, then uptitrated to 50 mg, weekly for 4 weeks Administered as a single SC injection once a week on the same day each week. Administered in the morning.	Study Part A: 10 μ g twice daily for 5±1 days Study Part B: 5 μ g twice daily for 4 weeks, then uptitrate to 10 μ g for 4 weeks Administered as a SC injection within the 60-minute period before the morning and evening meals (or before the two main meals of the day approximately 6 hours or more apart). Exenatide should not be administered after a meal

6.2. Treatment Assignment

Part A:

All subjects in Part A of the study will receive 10 μ g exenatide twice daily for 5±1 days.

Part B:

Randomized treatment assignment will be done via a web-based interactive response (IRT) system (RAMOS NG). Randomization will be centralized and will be implemented based on a randomization schedule generated by Clinical Statistics using RAMOS. Study center personnel will access the IRT to execute each randomization once a subject has

met all prerequisites for randomization and has completed all scheduled screening assessments.

Subjects will be assigned to study treatment in accordance with the randomization schedule. Eligible subjects will be stratified by screening HbA1c value (<7.5% and \geq 7.5%), and background use of OAM (OAM use versus no OAM use). Additional stratification may be added based on the results from Part A.

Subjects will be randomized in a 1:1 ratio to either open label albiglutide or exenatide.

Study centre personnel will receive a randomization notification indicating only the unique subject identifier, the treatment assignment, and the date and time of randomization. Each subject number will be a unique identifier. Once a subject number has been assigned, the number will not be reused even if the subject withdraws before receiving any study treatment.

6.3. Planned Dose Adjustments

Part A:

There is no dose titration for Part A of this study.

Part B:

Subjects will receive 30 mg of albiglutide once weekly during Weeks 1-4 and will then be up-titrated to 50 mg albiglutide once weekly at Week 5 for the remainder of the study.

Subjects will receive 5 μ g of exenatide twice daily during Weeks 1-4 and will then be up-titrated to 10 μ g exenatide twice daily at Week 5 for the remainder of the study.

Down-titration (dose reduction) of albiglutide and exenatide is **NOT** permitted. If a subject experiences tolerability issues with the higher doses then the subject may be withdrawn from the study at the discretion of the investigator.

6.4. Blinding

This will be a treatment open-label study.

The reviewers/readers of EGG and individuals who perform sample testing and data production for GEBT will be blinded to randomized treatments. The study team will remain blinded to the treatment assigned group for the assessment of safety aggregate data. If an interim analysis is conducted (see Section 9.2.3.2.), the study team may be unblinded to the aggregate data.

6.5. Packaging and Labeling

Exenatide and albiglutide are marketed products. Exenatide will be sourced locally. Clinical image albiglutide pens will be provided. The contents of the label will be in accordance with all applicable regulatory requirements.

6.6. Preparation/Handling/Storage/Accountability

No special preparation of study treatment is required other than that described in Section 6.1

Only subjects enrolled in the study may receive study treatment and only authorized site staff may supply or administer study treatment. All study treatments must be stored in a secure environmentally controlled and monitored (manual or automated) area in accordance with the labelled storage conditions with access limited to the investigator and authorized site staff.

The investigator, institution, or the head of the medical institution (where applicable) is responsible for study treatment accountability, reconciliation, and record maintenance (i.e. receipt, reconciliation and final disposition records).

Further guidance and information for final disposition of unused study treatment are provided in the Study Reference Manual (SRM).

Under normal conditions of handling and administration, study treatment is not expected to pose significant safety risks to site staff. Take adequate precautions to avoid direct eye or skin contact and the generation of aerosols or mists. In the case of unintentional occupational exposure notify the monitor, Medical Monitor and/or GSK study contact.

A Material Safety Data Sheet (MSDS)/equivalent document describing occupational hazards and recommended handling precautions either will be provided to the investigator, where this is required by local laws, or is available upon request from GSK.

6.7. Compliance with Study Treatment Administration

Accountability will be done for the investigational product (albiglutide) and other study treatments (exenatide) at the time points specified in the Time and Events Table (Section 7.1) Subjects will be instructed to return all unused investigational product and used injector pens in order to perform drug accountability and determine compliance.

Acceptable overall compliance for IP (albiglutide) and other study treatments (exenatide) in this study will be $\geq 80\%$. Site personnel should confirm that subjects are taking their doses of albiglutide or exenatide, if appropriate, as prescribed by their physician. Adherence will be monitored for the duration of the study.

When subjects are dosed at the site, they will receive study treatment directly from the investigator or designee, under medical supervision. The date and time of each dose administered in the clinic will be recorded in the source documents.

When subjects self-administer study treatment(s) at home, subjects will be instructed to return all unused investigational product and used injector pens. Compliance with albiglutide or exenatide will be assessed through a count of the returned injector pens and as reported by the subject. Compliance will be documented in the source documents and eCRF. Treatment start and stop dates, including dates for treatment delays will also be recorded in the eCRF.

6.8. Treatment of Study Treatment Overdose

In the event of an overdose the investigator should:

- Contact the Medical Monitor immediately.
- Closely monitor the subject for AEs/serious adverse events (SAEs) that may be related to treatment overdose (see below). The appropriate supportive clinical care should be instituted, as dictated by the subject's clinical signs and symptoms.
- Document the quantity of the excess dose as well as the duration of the overdosing in the eCRF.

Decisions regarding dose interruptions or modifications will be made by the investigator in consultation with the Medical Monitor based on the clinical evaluation of the subject.

6.8.1. Albiglutide

No data are available with regard to albiglutide overdose in humans. The highest recommended dose of albiglutide is 50 mg once weekly.

During clinical studies of subjects with T2DM, the highest dose of albiglutide administered was 100 mg subcutaneously every 4 weeks for 12 weeks. This dose was associated with an increased frequency of nausea, vomiting, and headache.

Anticipated symptoms of an overdose may be severe nausea, vomiting or headache. A prolonged period of observation and treatment for these symptoms may be necessary, taking into account the half-life of albiglutide (5 days).

There is no specific antidote for overdose with albiglutide.

6.8.2. Exenatide

In a clinical study of exenatide, three patients with T2DM each experienced a single overdose of 100 µg SC (10 times the maximum recommended dose). Effects of the overdoses included severe nausea, severe vomiting, and rapidly declining blood glucose concentrations. One of the three patients experienced severe hypoglycemia requiring parenteral glucose administration. The three patients recovered without complication.

Refer to the exenatide US PI for further details.

6.9. Treatment after the End of the Study

Investigational product will not be provided to subjects by GSK after the end of the study. In Part A, the last dose of exenatide will be in the morning before the GEBT on Day 5±1. In Part B, the last dose of exenatide will be in the morning before the GEBT of Week 8 Day 4±1. The last dose of albiglutide will be on Week 8 Day 1.

The investigator is responsible for ensuring that consideration has been given to the post-study care of the subject's T2DM. After the last dose of albiglutide or exenatide, the investigator will provide subjects with instructions of how to continue to treat their

T2DM after the end of the study. The half-life of his/her study treatment (albiglutide/exenatide) should be taken into consideration.

- The half-life of albiglutide is approximately 5 days, and significant therapeutic concentrations can persist for 3 to 4 weeks after discontinuation. The choice of other medicinal products and dose selection should be considered accordingly, as adverse reactions may continue and efficacy may, at least partly, persist until albiglutide levels decline.
- The half-life of exenatide is 2-3 hours.

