7. Details of full and brief physical examinations are provided in Section 7.4.3.
8. Only related to study participation SAEs
9. The GCSI-DD questionnaire will be completed after the standard AE questions have been answered.
10. Clinical chemistry, hematology, urinalysis and lipid assessments are described in Section 7.4.6. Lipids will be assessed at screening only.
11. Creatinine for eGFR only
12. Subjects will be provided with diet and exercise guidance (see Section 7.4.8) and instructed on self monitoring blood glucose at screening (See Section 7.4.9). Subject will be instructed to bring in their glucometers at each visit for review. Diet/exercise/SMBG reinforced at subsequent visits.
13. Informed consent for optional Genetic research should be obtained before collecting a sample.
14. On the morning of Day 1, after baseline EGG test, subjects will receive instructions and training on exenatide or albiglutide self administration and will be monitored by medical staff at the clinic during administration of the first dose. The first dose of will be administered after the baseline EGG procedure and before the post-procedure meal.
15. On Day 29 (± 1 day), study treatment will be uptitrated to 10 μ g twice daily exenatide or 50 mg once weekly albiglutide (see Section 6.3). Subjects will receive instructions and training on exenatide or albiglutide self administration and will be monitored by medical staff at the clinic during administration of the first dose.
16. Every effort should be made to schedule the procedures on the nominal visit day identified. However, in order to meet scheduling needs, subjects taking OAM can schedule Day-1 up to 3 days prior to Day 1 and the OAM stopped at least the day before the GEBT . For subjects treated with diet and exercise alone Day-1 can occur within 7 days prior to Day 1. The EGG and GEBT should not be scheduled on the same day.

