7.3. EGG and GEBT Test

GEBT and EGG measurements will be undertaken in the clinic and performed on separate days. Measurements for both Part A and Part B will be taken at the time points specified in the Time and Events Table in Section [7.1](#). Clinical visits for EGG and GEBT will have a visit window of ± 1 day and should be planned to avoid days of expected holidays, weekends and vacations.

- Albiglutide should be self-administered in the morning 3 ± 1 days before the EGG procedure.
- Exenatide should be self-administered twice daily. In the morning of each test day, subjects should be instructed NOT to self-administer exenatide at home. The morning dose of exenatide on the day of in-clinic test must be administered by the site staff. The dose of exenatide should be administered 1 hr ± 15 min prior to the start of the EGG or GEBT procedure. Every effort should be made to administer at the same pre-procedure time at each visit for the same subject.

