	Day -21 to -4	Day -3 to -5	Day -1 ¹³	Day 1	Day 2	Day 3	Day 4 ± 1 day ¹³	Day 5 ± 1 day ¹³

2. For subjects taking OAM at screening only. **At a minimum**, two day washout for immediate release and **at minimum** 4 day washout for extended release OAMs. **See footnote 13.** For information on restarting OAM refer to Section 6.9

13 Every effort should be made to schedule the procedures on the nominal visit day identified. However, in order to meet scheduling needs, subjects taking OAM can schedule Day-1 up to 3 days prior to Day 1 and the OAM stopped at least the day before the GEBT . For subjects treated with diet and exercise alone Day-1 can occur within 7 days prior to Day 1. The EGG and GEBT should not be scheduled on the same day.

Table 3 Time and Events Table Study Part B (only amended rows are shown)

Procedures	Screening/Wash-Out Period (0-3 weeks)			Treatment Period (exenatide or albiglutide) (8 weeks)									Un scheduled	Early Withdrawal	Follow-Up	
	-3 to -1	-1 ¹⁶		1	2 ¹⁶	3	4	5 ¹⁶			6	7	8 ¹⁶			
Study Week	-3 to -1	-1 ¹⁶		1	2 ¹⁶	3	4	29±1	31±1	32±1	-	-	52±1	53±1	12	
Study Day	-21 to -4	-3 to -5	-1	1	10±1	-	-									78-84±3
Study Visits	1		2	3	4			5	6	7			8	9		10
OAM washout ²		X														
Height, Weight, BMI	X												X ⁶		X ⁵⁶	
FPG	X		X	X	X			X	X	X			X	X		X
capillary blood glucose at clinic			X	X	X			X	X	X			X	X		X

2. For subjects taking OAM at screening only. **At a minimum**, two day washout for immediate release and **at minimum** 4 day washout for extended release OAMs. See footnote 16. For information on restarting OAM refer to Section 6.9

16 Every effort should be made to schedule the procedures on the nominal visit day identified. However, in order to meet scheduling needs, subjects taking OAM can schedule Day-1 up to 3 days prior to Day 1 and the OAM stopped at least the day before the GEBT. For subjects treated with diet and exercise alone Day-1 can occur within 7 days prior to Day 1. The EGG and GEBT should not be scheduled on the same day.

Section 7.3**EGG and GEBT**

GEBT and EGG measurements will be undertaken in the clinic **and performed on separate days**. Measurements for both Part A and Part B will be taken at the time points specified in the Time and Events Table in Section 7.1. Clinical visits for EGG and GEBT will have a visit window of ± 1 day. ~~At the Week 5 and 8 visits, the EGG must be performed the day before the GEBT~~ and should be planned to avoid days of expected holidays, weekends and vacations.

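### Section 6.9 and the pre-EGG dosing instructions conflict if the final GEBT precedes the final EGG, an order the visit windows allow in one day pair

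*Protocol*

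**What the plan says.** **End of exenatide.** Protocol Section 6.9 defines the last dose by the GEBT, not by the last test of either kind. For Part A: "In Part A, the last dose of exenatide will be in the morning before the GEBT on Day 5±1". For Part B: "In Part B, the last dose of exenatide will be in the morning before the GEBT of Week 8 Day 4±1". The same section states: "The half-life of exenatide is 2-3 hours".

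**Dose before each test.** Section 7.3, which covers both parts, states: "The dose of exenatide should be administered 1 hr ± 15 min prior to the start of the EGG or GEBT procedure". Footnote 12 of the Part A schedule (Table 2) and footnote 5 of the Part B schedule (Table 3) repeat this, and both are marked on the final EGG as well as the final GEBT.

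**Timing and order.** Section 7.3 gives each test its own window ("Clinical visits for EGG and GEBT will have a visit window of" ±1 day). Footnotes 13 and 16 add: "The EGG and GEBT should not be scheduled on the same day". Nominally the EGG comes first: Day 4 then Day 5 in Part A, Day 52 then Day 53 at Week 8. The same footnotes ask sites to make every effort to keep the nominal day. No current text requires the EGG to come first. Appendix 9 shows a sentence deleted by Amendment 1: "At the Week 5 and 8 visits, the EGG must be performed the day before the GEBT". That deletion is not an error; it only confirms that no order rule is in force at Week 8.

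**Purpose.** Section 4.4 plans the EGG and GEBT at expected Cmax.

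**The concern.** Two sets of instructions answer the same question, whether exenatide is given before the final EGG. They agree when the EGG comes first. When the GEBT comes first, Section 6.9 says dosing has already ended, while Section 7.3 and the footnotes call for another dose.

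The final EGG carries weight in both parts. In Part A it is the only EGG on treatment, and Section 4.2 makes progression to Part B depend on EGG showing a change caused by exenatide. In Part B it is one of the three primary visits (Section 9.2.4.1). If sites resolve the conflict differently, records under one visit label come from different dosing states. Those taken after dosing ended would pull the exenatide effect at that visit toward zero, to the extent that the effect fades with the drug.

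The RAP would not exclude them. Its definition of an evaluable subject (Section 1, Planned Analyses) needs one valid EGG before and one after dosing, with no maximum interval from the last dose.

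**Working it through.** **Inputs**
- Last exenatide dose: morning of the final GEBT (Protocol 6.9).
- Part A: EGG Day 4±1, GEBT Day 5±1 (Table 2).
- Part B, Week 8: visits on Day 52±1 and Day 53±1 (Table 3). The columns are broken in the extracted text, so EGG on Day 52 is inferred from Section 6.9.
- Pre-test dose: 1 h ± 15 min before either test (7.3, footnotes 5 and 12).
- Exenatide half-life: 2-3 h (6.9).

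**1. The plan's own day.** Study day = 7 × (week − 1) + day. Week 8 Day 4 = 7 × 7 + 4 = 53. This matches Table 3, so Sections 6.9 and 7.1 agree on the nominal GEBT day.

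**2. Permitted day pairs.** Each test has three possible days, giving 3 × 3 = 9 pairs. Two fall on the same day and are barred, leaving 7.

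| Part A EGG | GEBT days allowed | Part B EGG | GEBT days allowed |
|---|---|---|---|
| Day 3 | 4, 5, 6 | Day 51 | 52, 53, 54 |
| Day 4 | 5, 6 | Day 52 | 53, 54 |
| Day 5 | **4**, 6 | Day 53 | **52**, 54 |

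One pair of seven in each part has the GEBT first (bold), by exactly one day. This is a count of permitted schedules, not a probability.

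**3. The reversed pair under each instruction.** Half-lives elapsed = interval / half-life; fraction left = 2^(−half-lives), assuming first-order elimination.

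| Instruction applied | Time from dose to EGG | Half-lives | Fraction left |
|---|---|---|---|
| 6.9 (dosing ended with the GEBT) | about 24 h | 24/3 = 8 to 24/2 = 12 | 0.39% to 0.024% |
| 6.9, dose 1 h before GEBT, EGG at the same clock time next day | 25 h | 25/3 = 8.3 to 25/2 = 12.5 | 0.31% to 0.017% |
| 7.3 and footnotes 5/12 | 0.75 to 1.25 h | 0.75/3 = 0.25 to 1.25/2 = 0.63 | not an off-drug record |

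Section 2.1 gives an exenatide Tmax of about 2.1 h. An EGG a day after the last dose therefore misses the Cmax timing planned in Section 4.4.

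**4. Effect on the arm mean.** Let f be the share of exenatide subjects whose final EGG is both reversed and recorded under 6.9. Assume equal effects across subjects and none persisting off drug. The arm mean at that visit then keeps (1 − f) of its effect. The documents give no value for f, so it could be anything from 0 to 1. Per affected subject, the loss is 1/10 = 10% of the mean effect with the planned 10 or so evaluable subjects in Part A, and 1/25 = 4% with the planned 25 per arm in Part B.

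**5. With the EGG on the earlier day.** The remaining six pairs all have the EGG before the GEBT, and in none of them does the EGG fall after the Section 6.9 last dose.

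**The case against.** The strongest reply is that the windows alone do not produce an off-drug EGG. A site would have to set aside a test-day instruction, given in Section 7.3 and marked on the final EGG itself, in favour of a sentence in a section on care after the study. The order must also reverse, with both tests moved off their nominal days in opposite directions, although sites are asked to keep those days. All of this stands, and it limits the point to a contradiction in one permitted pair.

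Three stronger readings are tempting, and the documents do not support them.

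- **That the albiglutide interval makes the reversed order natural.** Footnote 5 asks for the EGG 3±1 days after the albiglutide dose, and Day 50 + 3 = Day 53. That interval concerns albiglutide subjects only, and it also permits Day 52. It does not move an exenatide subject's EGG.
- **That the Week 8 contrast compares treated with untreated subjects.** That would require every exenatide subject to be affected (f = 1).
- **That a particular percentage dilution can be stated.** Nothing in the documents gives f.

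It is also fair to say that Part A is descriptive, with about 10 evaluable subjects, and that the RAP covers Part A only, reports early termination and plans listings for the exploratory endpoints. This lowers the practical impact but does not remove the contradiction. The RAP's convention of showing times relative to dosing (Section 5.1) would help to identify such records.

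**Conclusion.** The contradiction is real but narrow. Section 6.9 cannot be followed together with Section 7.3 and footnotes 5 and 12 when the final GEBT precedes the final EGG. The current windows allow that in one of seven different-day pairs in each part. In that pair the exenatide EGG falls either about 24 h after the last dose (8 to 12 half-lives) or about 1 h after a dose, depending on which instruction the site applies.

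Only exenatide subjects are exposed, and only at the last EGG. Weeks 2 and 5 are unaffected because dosing continues. The albiglutide arm is unaffected because its last dose is fixed at Week 8 Day 1. The share of subjects affected is unknown, so no overall bias can be quoted.

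The conclusion assumes that the Week 8 EGG is nominally on Day 52, that tests on consecutive days start at similar clock times, and that elimination is first-order. The documents do not settle which instruction prevails, and this review takes no view on that.

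**What to change.** Reconcile Section 6.9 with Section 7.3 and footnotes 5 (Part B) and 12 (Part A), so that the final EGG and the final GEBT are made in the same dosing state. The sponsor decides which passage to amend.

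One option leaves the dosing text untouched: state in Section 7.3 and the schedule footnotes that, in Part A and at Week 8, the final EGG is done on an earlier day than the final GEBT. This removes one of the seven permitted pairs. It costs one sentence, the matching footnotes and a little of the scheduling flexibility that Amendment 1 sought.

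In the RAP, flag any final EGG recorded after the last exenatide dose day, using the recorded dose and test dates. For the Part A data already collected, this is one added flag in the EGG listing.
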